4.2.2 Blinding procedures

This section is not applicable.

4.2.3 Other methods for minimising bias

Confounding factors obscuring the 'real' effect of an exposure on outcome, will be controlled by inclusion and exclusion criteria. Attention is paid to equal gender distribution.

To minimize the bias of the evaluation of product performance, the evaluators who independently assess the restorations do not place any restorations and are also not informed about who the operator was. The restorations are all produced by the same PM 7 CAD/CAM system from experienced dental technicians. Therefore, an influence of different CAD/CAM systems on the quality of the restorations can be excluded. Five different operators will place the restorations. This is important in order to minimize the effect of the handling of one single operator on the quality of the restorations.

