Outcome(s):	
The primary endpoint of this clinical trial is the incidence rate of postoperative hypersensitivity. The assessment of the postoperative hypersensitivity is performed and graded according to the FDI criteria (Hickel et al. 2007; Hickel et al. 2010, Hickel et al. 2022).
 
The secondary outcomes are the vitality and fracture rate of restored teeth and the retention/fracture rate of restorations. These parameters provide information about the clinical performance of the bond of the restoration to the tooth structure. Another secondary outcome is the marginal quality of the restorations that also provides information about the quality of the bond between tooth structure and luting composite. The secondary outcomes will be assessed at all recalls with the respective FDI criteria (Hickel et al. 2022).

Design:	
This is a prospective single-arm clinical investigation. The safety and performance results of ██████████ will be compared with the coded data of the control group (Adhese Universal) of an already performed clinical investigation ("Clinical evaluation of a new dual cure universal adhesive (Adhese Universal DC) in the indirect restorative therapy: A randomised, controlled clinical trial", NCT04475679). The study design of the planned clinical investigation follows the design of the previously conducted clinical investigation. The objectives, outcome parameters and methods are the same.

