4.1 General clinical investigation design and justification of design

████████ a new dental adhesive will be used to lute 45 inlays or onlays out of e.max CAD to teeth of at least 23 patients.

This prospective study has only one group (████████) because the planned study is similar to a trial which has recently been executed in the internal clinic of Ivoclar Vivadent AG (NCT04475679). The only difference to the already performed study is the device under assessment. Therefore, the coded results of the control group of the previous clinical investigation (Adhese Universal) will be compared with the clinical performance of the new dental adhesive (████████).

There are 5 operators and 2 evaluators. All operators are very experienced dentists in the field of restorative dentistry. The treatment of restoring teeth with ceramic inlays or onlays is a standard treatment in the internal clinic of Ivoclar Vivadent AG.

Postoperative sensitivities arise within days after the treatment. Therefore, the occurrence of postoperative sensitivities can be assessed already at baseline. Final assessment of postoperative hypersensitivities will be performed at the 1-month recall. If such an incident is still present after 1 month, it will be followed regularly.

The study duration of 5 years corresponds to the minimal duration recommended in restorative dentistry (Hickel et al., 2022). The patients will attend a recall after 6-12 days (baseline), 1, 6, 12, 24, 36, and 60 months.

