5.1.2 Control Intervention (standard/routine/comparator)

This section is not applicable.

Data will be compared with coded results of the control group (Adhese Universal) of a previously conducted clinical investigation ("Clinical evaluation of a new dual cure universal adhesive (Adhese Universal DC) in the indirect restorative therapy: A randomised, controlled clinical trial", NCT04475679).

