6. STATISTICAL METHODS

The trial is a continuation of the clinical trial "Clinical evaluation of a new dual cure universal adhesive (Adhese Universal DC) in the indirect restorative therapy: A randomised, controlled clinical trial (NCT04475679)". The methodology, the endpoints and the hypothesis are the same. The test product [REDACTED] is a further development of Adhese Universal DC. In the planned clinical investigation, the test group will be compared to the control group (Adhese Universal) of the study mentioned above. The statistical considerations of the already performed study are re-used and are therefore mentioned in the paragraphs below.

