6.4.2 Primary Analysis

Regarding the primary outcome, the interim analysis will be done at baseline. The final analysis of the primary outcome will be done after completion of the 1-month recall. The analysis will be done by the principal investigator within 3 months after the collection of the 1-month data.

A non-parametric test (Mann-Whitney) between two independent groups will be used to compare the level of postoperative hypersensitivity (FDI 11) between the control and the test group.

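### The unadjusted Mann-Whitney test is carried over from a randomised trial to a non-randomised comparison with past controls, and eligibility criteria do not balance the two groups

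*Combined protocol and SAP*

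**What the plan says.** The synopsis (Design) and sections 4.1 and 5.1.2 describe one prospective arm, to be compared with the Adhese Universal group of a completed study. Section 5.1.2 gives that study's title, which includes "in the indirect restorative therapy: A randomised, controlled clinical trial". In the present study, section 4.2.1 marks randomisation as not applicable.

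Section 6 carries the analysis over: "The statistical considerations of the already performed study are re-used and are therefore mentioned in the paragraphs below". Section 6.4.2 then names the primary test: "A non-parametric test (Mann-Whitney) between two independent groups will be used to compare the level of postoperative hypersensitivity (FDI 11"). No section names a covariate, stratum, matching rule or weight. The only remark on adjustment, in 6.4.4, concerns interim looks.

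On confounding, 4.2.3 says: "Confounding factors obscuring the 'real' effect of an exposure on outcome, will be controlled by inclusion and exclusion criteria". It adds only that attention is paid to gender distribution. Section 4.1 asserts: "The only difference to the already performed study is the device under assessment". The relevant eligibility limit is a pre-operative VAS of at most 3 (synopsis, inclusion criteria).

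**The concern.** In a randomised trial an unadjusted rank test is valid because any imbalance is due to chance, and the type I error allows for chance. Here the groups come from two trials and two recruitment periods. A systematic difference in case mix is not covered by the type I error, and more teeth would not remove it.

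Eligibility criteria cut off the extremes of a confounder and leave its distribution inside the permitted range free. One group could consist mostly of symptom-free teeth and the other largely of teeth at VAS 1 to 3, with every tooth eligible. The same applies to age within 18 to 65, premolar or molar, inlay or onlay, and primary caries or replacement of a filling.

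The bias could run either way: it could create a difference or hide a real excess. The second matters more here, because 6.1 expects no significant difference, so a masked excess would look like the expected result. The form of the hypotheses in 6.1 is a separate matter and is not part of this point.

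**Working it through.** **Inputs from the plan.** Section 6.2 gives 40 teeth per arm, raised by 5 for dropout (40 + 5 = 45), and a type I error of 0.1 without sidedness. The 40 cannot be re-derived, because no effect size, rate or margin is given. It serves here only as the control group size.

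**Assumptions (none is in the documents).**
- Risk of any grade above 1 is p0 = 5% at pre-operative VAS 0, with risk ratio RR = 2, 3 or 4 above 0.
- The base share of teeth above VAS 0 is 30%, and one group is shifted up by 20 or 30 points.
- Teeth above grade 1 split 70/25/5% over grades 2, 3 and 4.
- Tests are two-sided at 0.10, tie-corrected normal approximation, 45 v 40 teeth.
- 6,000 runs per scenario. Monte Carlo standard error at 10%: sqrt(0.1 × 0.9 / 6000) = 0.39 points.

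**Step 1: spurious difference with no device effect.** Bias = p0 × (RR − 1) × shift.
- Smallest: 0.05 × 1 × 0.20 = 0.010.
- Largest: 0.05 × 3 × 0.30 = 0.045.
- Standard error at 10% incidence: sqrt(0.09 × (1/45 + 1/40)) = 0.0652.
- Ratios: 0.010/0.0652 = 0.15 and 0.045/0.0652 = 0.69.
- With each scenario's own incidences (7.5% v 6.5%; 14% v 9.5%) the ratios are 0.18 and 0.65.

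**Step 2: rejection with no device effect, teeth treated as independent.**

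| RR, shift | Unadjusted | Stratified by VAS 0 v above 0 |
|---|---|---|
| no shift | 10.2–10.7% | 9.8–10.4% |
| 2, +20 | 11.0% | 10.1% |
| 2, +30 | 11.2% | 9.9% |
| 3, +20 | 11.4% | 10.4% |
| 3, +30 | 12.6% | 9.6% |
| 4, +20 | 12.8% | 10.6% |
| 4, +30 | 15.7% | 10.1% |

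The effect is negligible at RR 2 and clear only at RR 4 with 30 points. A 10-point shift (40% v 30%) gives 10.3–10.8% for the unadjusted test at RR 1.5 to 4.

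**Step 3: masking.** The device doubles the risk, the test group has 30% of teeth above VAS 0, and the control group has 50% or 60%. At RR 4 the test risk is 2 × 0.05 × (1 + 0.3 × 3) = 19.0%. The control risk is 0.05 × (1 + 0.3 × 3) = 9.5% with no shift and 0.05 × (1 + 0.6 × 3) = 14.0% at 60%. The crude excess falls from 9.5 to 5.0 points.

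| RR, control share | Unadjusted detects | Stratified detects |
|---|---|---|
| 2, 30% (no shift) | 24.6% | 24.8% |
| 2, 50% | 20.1% | 26.7% |
| 2, 60% | 18.8% | 27.5% |
| 4, 30% (no shift) | 33.1% | 35.3% |
| 4, 50% | 20.8% | 40.4% |
| 4, 60% | 15.9% | 40.6% |

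Repeat simulations of the RR 4, 30-point scenarios agreed within about 1 point.

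**Step 4: two teeth per participant.** Neither test allows for this. With no shift and no device effect, within-participant ICC 0.2 gives 11.3–11.6% unadjusted and 10.7–11.6% stratified. ICC 0.5 gives 13.7–14.4% and 13.4–14.8%. Stratifying neither causes nor cures this.

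**The case against.** **The plan has real safeguards.** The comparator comes from the same setting: "the planned study is similar to a trial which has recently been executed in the internal clinic". The synopsis adds: "The objectives, outcome parameters and methods are the same". One CAD/CAM system is used, and "the evaluators who independently assess the restorations do not place any restorations and are also not informed about who the operator was". Other eligibility criteria also restrict sources of pulpal symptoms, such as irreversible pulpitis, direct pulp capping and recent bleaching. These points stand and make a 30-point shift the far end of the range. Most of them reduce differences in measurement and handling; none fixes the mix of teeth inside the eligible range.

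**Pre-operative VAS is the confounder the endpoint handles best.** Section 3.1 reads post-operative VAS against the pre-operative value, and grade 1 spans VAS 0 to 3, the same range as the eligibility limit. This absorbs part of any carry-over. It does not remove it: 3.1 also says VAS does not map directly to the grade, which rests on evaluator judgement, and grade 1 is also described by absence of complaint and of symptoms. Grading each tooth is not an adjustment of the group comparison.

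**The masking reference is not like for like,** because shifting the control share also adds control events. That is correct, but a matched reference makes the loss larger: with RR 4 and 45% above VAS 0 in both groups, the unadjusted test detects 39.5%, against about 16% under the shift.

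**The sentence in 4.1 may describe only the protocol, not the patients.** It can be read that way, but it is the stated reason for using the external control, so it should not leave out the change of trial and period.

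**Other problems are as large.** Clustering, period, operator and evaluators not blinded to the adhesive all remain. That limits what the fix achieves; it is no reason to leave a recorded baseline value unused.

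**Conclusion.** The concern holds. It is certain from the text that the comparison is non-randomised and non-concurrent, that the test is unadjusted, and that 4.2.3 claims more than eligibility criteria can deliver. The size of the harm is uncertain: the documents show no imbalance and give no control baseline data. Under the assumptions above, false rejection ranges from hardly changed to about half as high again as the nominal 10%. The larger risk is masking, where detection of a doubled risk can fall to less than half of what stratification gives (15.9% v 40.6%). Power is low either way, and few teeth above grade 1 are expected: 6.0 to 10.1 of 85 on average in the shifted scenarios without a device effect. This should be corrected before new-arm outcomes are seen, but it does not invalidate the study.

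**What to change.** 1. Check whether the coded control data hold pre-operative VAS per tooth; the documents only imply it. If they do, prespecify in 6.4.2 a Mann-Whitney test stratified by pre-operative VAS (van Elteren; higher of the thermal and biting values, 0 v above 0) as the comparison on which the conclusion rests, with the unadjusted test reported beside it. If they do not, keep the Mann-Whitney test and state that the comparison is unadjusted. Fix the choice before any new-arm outcome is seen, because the control outcomes already exist.
2. Tabulate pre-operative VAS (where held), tooth type, restoration type, operator, age and sex for both groups.
3. Replace the first sentence of 4.2.3 and the only-difference claim in 4.1. State that the comparison is non-randomised and non-concurrent, and that eligibility criteria and shared methods reduce confounding without controlling it. Word the conclusion to match.

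The cost is one data check, one stratified test, one table and two sentences. Pre-operative VAS is already scheduled before luting, so no visit or measurement is added. Stratifying costs under 2 points of detection when VAS is not prognostic. Section 6.4 names only SPSS 25: confirm that it runs the test, or state that it will be computed from within-stratum rank sums. With no device effect and ICC 0 or 0.2, each test was undefined in at most 0.32% of simulated runs, so no outcome-dependent fallback is needed.

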4.3 Unblinding Procedures (Code break)

None, as no blinding procedures are applied.

5. CLINICAL INVESTIGATION INTERVENTION

5.1 Identity of the medical device under investigation

5.1.1 Experimental Intervention (medical device)

The newly developed dental adhesive [REDACTED] will be used together with a cement for luting an indirect restoration on tooth structure.

[REDACTED] is a dual-curing single-component dental adhesive for enamel and dentin that is compatible with all etching techniques (self-etch, selective-enamel-etch, etch & rinse techniques). The product is indicated for both indirect restorations and direct restorations. In this clinical investigation, [REDACTED] in the VivaPen® (primary packaging) is used. VivaPen DC cannula (blue) is coated with the co-initiator required for the self-curing reaction. For hygienic reasons, a VivaPen protective sleeve is used by sliding the Pen with the cannula into the protective sleeve until the cannula punctures through the sleeve (Fig. 1). As described in the IFU, a new cannula and protective sleeve must be used for each patient. The [REDACTED] VivaPen can be re-used. By pressing the VivaPen push button (blue), the flocked cannula tip is saturated with adhesive liquid and mixes with the co-initiator. Following activation, the adhesive can be applied for approx. 120 seconds. Starting with the enamel the tooth surfaces to be treated need to be completely coated with [REDACTED]. The adhesive must be scrubbed onto the tooth surface for at least 20 seconds. Then [REDACTED] is dispersed with oil- and moisture-free compressed air until a glossy, immobile film layer result. Since [REDACTED] is a dual curing material, it does not need to be light cured after application. Most adhesives on the market must be light cured. The application without light curing is of interest for this trial. The application of the material is in accordance with the instruction for use.

A)

B)

Fig 1: A) [REDACTED] delivered in the VivaPen with the blue cannula for the dual curing adhesive and B) VivaPen with protective sleeve.

5.1.2 Control Intervention (standard/routine/comparator)

This section is not applicable.

Data will be compared with coded results of the control group (Adhese Universal) of a previously conducted clinical investigation ("Clinical evaluation of a new dual cure universal adhesive (Adhese Universal DC) in the indirect restorative therapy: A randomised, controlled clinical trial", NCT04475679).

6. STATISTICAL METHODS

The trial is a continuation of the clinical trial "Clinical evaluation of a new dual cure universal adhesive (Adhese Universal DC) in the indirect restorative therapy: A randomised, controlled clinical trial (NCT04475679)". The methodology, the endpoints and the hypothesis are the same. The test product [REDACTED] is a further development of Adhese Universal DC. In the planned clinical investigation, the test group will be compared to the control group (Adhese Universal) of the study mentioned above. The statistical considerations of the already performed study are re-used and are therefore mentioned in the paragraphs below.

6.1 Hypothesis

The null hypothesis is that there is a statistically significant difference between control and test group with respect to postoperative hypersensitivity.

The alternative hypothesis is that there is no difference between control and test group with regard to postoperative hypersensitivity.

We do not expect in this equivalence study to find any statistical significance between control and test group with regard to postoperative hypersensitivity.

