Registration:	
Registry at ClinicalTrials.gov of the U.S. National Library of Medicine (http://www.clinicaltrials.gov)
 
The trial gets registered in the supplementary federal database (Portal for clinical trials in Switzerland - SNCTP, https://www.kofam.ch/en/snctp-portal/) upon its submission on BASEC.
 
As soon as the new electronic system EUDAMED is operational, the clinical investigation will be retrospectively registered, if required.

Category and its rationale:	
Category C2 (Art. 6 ClinO-MD)
 
The medical device has no conformity marking.

Name of the MD, Unique Device Identification (UDI), name of the manufacturer	
████████ in VivaPen + VivaPen DC (dual-curing) cannula
 
UDI not available
 
Manufacturer: Ivoclar Vivadent AG [name] Liechtenstein

Stage of development:	
Pivotal stage
 
The clinical investigation is conducted for a conformity assessment purpose.

Background and rationale:	
The usage of a dental adhesive to lute ceramic inlays or onlays to teeth is necessary and state of the art to replace missing tooth structure. The investigational product ██████████ is a novel universal dual-cure adhesive. This clinical investigation is conducted to prove the clinical performance and safety of this new dental adhesive.

Objective(s):	
The overall aim of this study is to evaluate the clinical performance and safety of the dental adhesive ██████████ for luting indirect ceramic restorations (inlays and onlays). The investigation seeks primarily to determine the rate of postoperative hypersensitivity occurrence after using ██████████ for the placement of indirect restorations. The secondary objective of this study is to assess the long-term clinical performance of ██████████ in terms of marginal quality, retention/fracture rate of the ceramic restorations, and vitality/fracture rate of the restored teeth.

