Measurements and procedures:	
After information and written informed consent the participants will receive a dental treatment in relation to the restorative indication (caries, tooth/restoration fracture, insufficient restoration, etc), which means that the inlay/onlay cavity will be prepared and a digital impression with an intraoral scanner (Trios 3Shape) will be taken. Then, the cavities will be temporarily restored with provisional restorations. The scans will be sent to the lab where dental technicians will provide the final restorations made of lithium disilicate e.max CAD. In the following appointment the final restorations will be luted and final corrections as well as the finishing and polishing procedures will be done.
 
The baseline recall will take place 6-12 days after the insertion of the restoration. At the baseline recall the study specific parameters will be evaluated according to the FDI criteria ranging from 1 excellent to 5 clinically not acceptable.
 
Further recalls will be performed at 1, 6, 12, 24, 36 and 60 months after placement of the restoration.

Intervention:	
After getting a tooth which is in a need of a restoration (inlay or onlay), the cavity will be prepared, and an optical impression is taken. Then provisional restoration is cemented during the time, which is necessary to produce the indirect restoration in the dental lab. This first treatment appointment takes around 2.5 h. In a second treatment appointment the indirect ceramic restoration is luted to the tooth surface by the investigational product [REDACTED] and the well-established luting composite Variolink Esthetic DC. This will take at maximum 2 hours. During the baseline appointment a repolish of the restoration can be done by the operator before the evaluator assesses the restoration and the tooth. This will take at maximum 30 minutes. All following recall visits will take no longer than 30 minutes.

Control intervention (if applicable):	n.a.
Number of subjects with rationale:	45 teeth, at maximum two teeth per participant according to the statistical considerations.
Duration of the investigation:	5 years

Investigation schedule:	October 2024 First- subject –In (planned) April 2031 of Last- subject –Out (planned)

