6.2 Determination of Sample Size

The number of samples estimated to be needed for each study arm is 40 to achieve the objective. The G*Power sample calculator software Version 3.1.9.2 was used to determine the sample size, at a power of 80% and a type I error of 0.1 (Faul et al., 2007; Faul et al., 2009).

Different to the previous study, this time a drop-out of 5 restorations is assumed. Therefore, the sample size aimed at is 45 instead of 40.

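### Section 6.1 sets no direction for a harm endpoint, so significantly less hypersensitivity than the control falls under the null and does not count as success

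*Combined protocol and SAP*

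**What the plan says.** The synopsis (Outcome(s)) names a harm as the primary endpoint: "The primary endpoint of this clinical trial is the incidence rate of postoperative hypersensitivity". Grades are assigned "according to the FDI criteria ranging from 1 excellent to 5 clinically not acceptable" (synopsis, Measurements and procedures), so lower is better.

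Section 6.1 states the null as: "The null hypothesis is that there is a statistically significant difference between control and test group with respect to postoperative hypersensitivity". It states the alternative as: "The alternative hypothesis is that there is no difference between control and test group with regard to postoperative hypersensitivity". It adds: "We do not expect in this equivalence study to find any statistical significance between control and test group". None of the three sentences gives a direction or a margin.

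Section 6.4.2 says that a Mann-Whitney test "will be used to compare the level of postoperative hypersensitivity (FDI 11) between the control and the test group". It does not say whether the test is one- or two-sided. Section 6.2 gives 40 per arm "at a power of 80% and a type I error of 0.1", again without sidedness, and raises this to 45 for dropout.

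Two other places bear on direction. The synopsis (Background and rationale) gives the purpose: "This clinical investigation is conducted to prove the clinical performance and safety of this new dental adhesive". The hypersensitivity stopping rule in section 6.3 is triggered only by too many affected teeth.

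**The concern.** For a harm, a lower rate with the new adhesive is good news. Section 6.1 nevertheless groups a significantly lower rate with a significantly higher one, and treats only the absence of a difference as favourable. Nothing else in section 6 says that a lower rate counts as success.

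Adding a margin and a proper equivalence test would not remove this feature. The lower equivalence bound would still turn away a product that is better by more than the margin.

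At stake is whether the pivotal result can be read at all if the new adhesive does better than the control. Changing the definition of success after such a result would look post hoc.

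**Working it through.** **The plan's own figure.** The 40 per arm cannot be reproduced, because no effect size, rate, standard deviation or margin is given. Solving backwards at alpha 0.1 and 80% power, 40 per arm corresponds to a standardised difference of about 0.475 (t-test) to 0.49 (Mann-Whitney) if one-sided, and 0.556 to 0.57 if two-sided. An assumed difference of 0.5 needs 39 per arm one-sided or 53 two-sided with the Mann-Whitney test. The 40 may therefore be a one-sided figure, but this cannot be confirmed. The dropout step adds up: 40 + 5 = 45.

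**Inputs for the checks.** From the documents: 45 test teeth, 40 control teeth (the planned arm size) and alpha 0.1. Assumed: hypersensitivity reduced to yes/no, true rates, margin, independent teeth and no dropout.

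**Check 1: can a better adhesive land in the null?** Take the Mann-Whitney test as two-sided. With yes/no data the tie-corrected statistic is

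z = (t/45 − c/40) / √[p̄(1 − p̄)(1/45 + 1/40)(85/84)], with p̄ = (t + c)/85.

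For t = 0 and c = 3: p̄ = 3/85 = 0.0353, the denominator is 0.0403, z = −0.075/0.0403 = −1.86 and p = 0.063. With c = 4, p = 0.031; with c = 6, p = 0.007. All three are below 0.1 although no test tooth is affected.

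The chance of a significant difference in favour of the test product is the sum of Bin(t; 45, pT) × Bin(c; 40, pC) over all (t, c) with z < −1.645:

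| Assumed true rates, test v control | Chance |
|---|---|
| 2% v 5% | 15% |
| 5% v 10% | 23% |
| 2% v 10% | 49% |
| 2% v 15% | 76% |

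**Check 2: is power lost in the plan as written?** No equivalence test or margin exists, so no equivalence power is defined. With truly equal arms, a non-significant result occurs about 90% of the time (1 − 0.1), whether the test is one- or two-sided.

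**Check 3: if 6.1 were repaired as a true equivalence test.** Use Agresti-Caffo limits: d ± 1.2816 × SE at one-sided 10%, with pT = (t + 1)/47, pC = (c + 1)/42, d = pT − pC and SE = √[pT(1 − pT)/47 + pC(1 − pC)/42]. Non-inferiority requires the upper limit to be below the margin. Equivalence also requires the lower limit to be above minus the margin.

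Example, 0/45 v 4/40: d = 0.0213 − 0.1190 = −0.0978, SE = 0.0542, and the limits are −16.7 and −2.8 points. With a 15-point margin, non-inferiority is met and equivalence is not.

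Enumerating all tables in the same way (non-inferiority v equivalence, one-sided 10%):

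| True rates, test v control | 10-point margin | 15-point margin | 20-point margin |
|---|---|---|---|
| 2% v 2% | 95% v 85% | 99.8% v 99.2% | both above 99.9% |
| 10% v 10% | 61% v 21% | 86% v 69% | 97% v 93% |
| 5% v 10% | 92% v 25% | 99% v 62% | 99.9% v 89% |

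**The case against.** Equivalence is a legitimate design. Section 6.1 names it, and section 6 carries the hypothesis over from the earlier trial. Section 2.2 says only that results will be compared with the control. The one-sided question is therefore an inference from the safety purpose and the harm-only stopping rule, and the documents do not state it. That stands.

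A reader might infer that the plan already wastes power on excluding a benefit. The documents do not support this. There is no lower bound, margin or equivalence test in which power could be lost. If the 0.1 is two-sided, a one-sided 0.1 test with the same teeth would raise power to detect harm from 80% to 88.6%. If it is already one-sided, nothing is lost.

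A reader might also infer that the product would formally fail. No section attaches a consequence to a favourable difference; the termination rules in 6.3 concern failure and hypersensitivity only. The defect is that the hypothesis gives such a result no favourable reading.

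The direction is not the largest fault in 6.1. The null is worded as a significance finding, and a non-significant difference test would be taken as evidence of equivalence. One-sided wording without a margin and a confidence limit would not cure that.

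Finally, the control is historical, and the comparison is neither randomised nor blinded. A lower rate could reflect period or evaluator differences, so there is some value in noticing differences in both directions. This argues against a superiority claim. It does not argue for counting a lower rate against the product.

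**Conclusion.** The point holds for direction. Section 6.1 gives no direction for a harm endpoint and, read literally, puts significantly less hypersensitivity under the null. If the test is two-sided at 0.1, three affected control teeth against none of 45 are enough (p = 0.063). The chance of a favourable difference is 15% to 76% over the assumed rates.

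The point does not extend to a power loss in the current plan. The advantage of non-inferiority arises only against a true equivalence test with the same margin, and its size depends on the unknown control rate and margin. At 15 points it ranges from negligible when both rates are 2% to 17 percentage points when both are 10% (86% − 69%), and it is larger if the test product is truly better.

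All these figures rest on assumed rates and margins and on independent teeth, although two teeth per participant are allowed. The change is worth making before any comparison with the control.

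**What to change.** - **6.1:** restate as one-sided non-inferiority. H0: hypersensitivity incidence, test minus control, is at least the margin. H1: it is below the margin. Delete the sentence that expects no statistical significance.
- **6.4.2:** base the decision on the upper confidence limit of that difference, at the type I error in 6.2 and with its sidedness stated, so that a lower rate counts as success.
- **Before any comparison with the control:** the sponsor fixes the margin and the FDI grade from which a tooth counts as a case.
- **6.2 and the opening of 6:** restate the basis for 40 per arm, and correct the statement that the hypothesis is the same as in the earlier trial.
- **Reporting:** make no superiority claim against this historical control; describe a lower rate without a test claim.

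The cost is protocol and SAP wording plus a new sample-size justification. The repair itself adds no teeth or visits, but a narrow margin may prove hard to support with 45 v 40 teeth (61% power at 10 points when both rates are 10%). The sponsor would claim that the product is not worse than Adhese Universal, and would give up the claim of equivalence. If equivalence is needed, the plan should say so and justify the lower bound.
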